The major objective of this protocol is a therapeutic one, namely to establish the safety and efficacy of TPTD in premenopausal women with IOP in a phase 2 clinical trial. We hypothesize that osteo-anabolic therapy with TPTD will improve areal and vBMD in premenopausal women with IOP. We also hypothesize that TPTD will restore abnormal microarchitecture toward normal and improve other aspects of bone quality in premenopausal women with IOP. The primary aim of this research study will be to establish the efficacy and safety of 6 months of TPTD versus placebo in premenopausal women with IOP. Secondary aims are to determine the extent to which 12 and 24 months of TPTD improves areal and volumetric BMD, bone microarchitecture and stiffness compared to baseline measures in premenopausal women with IOP and to determine whether baseline bone turnover, as assessed by quadruple tetracycline labeling predicts response to TPTD. This study will have high impact on clinical practice as it pertains to the management of premenopausal women with IOP. This study is exploratory and will not support any new labeling claims for Forteo in the premenopausal patient population.

For the sub-study: We aim to investigate the pharmacokinetics (pK) and pharmacodynamics (pD) of teriparatide (Forteo) to determine if subject weight influences pK or pD. To develop preliminary data necessary to plan larger studies on this issue, we aim to study 6 subjects already enrolled in this study (AAAF2251) who are already in the open label treatment period. We will enroll 3 normal weight subjects (BMI between 18.5 kg/m2 and 24.9 Kg/m2) and 3 overweight or obese subjects (BMI equal to or greater than 25 kg/m2). All subjects will be offered participation until enrollment goals for the sub-study will be met.

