randomized, double blind, placebo-controlled, single switch-over trial of TPTD in premenopausal women with IOP. Forty-one subjects will be assigned to TPTD (Group A; n=28) or placebo (Group B; n=13). At the 6 month timepoint, all subjects will receive TPTD, but blinding of original group assignment will be maintained for an additional 6 months. At the 12 month visit, the blind will be broken and those initially randomized to TPTD (Group A) will continue on study drug for an additional 12 months while those initially randomized to placebo (Group B) will continue for an additional 18 months, so that subjects in both groups complete 24 months of treatment overall. aBMD by DXA and HRpQCT will be measured at baseline and at 6 month intervals. vBMD by cQCT will be performed before randomization and after 24 months of TPTD (Table 1). A quadruple labeled transiliac crest bone biopsy will be performed at 3 months for both Group A and B. Eli Lilly & Company will provide TPTD and placebo but will supply no other funding. After 24 months of treatment in either Group A or B, all women will be offered three choices for follow up: the subjects can A) continue to to be followed for 12 months off TPTD B) choice to leave the study and be treated clinically using an anti-resorptive medication to maintain gains in bone density after treatment with TPTD, or C) join a new study to maintain gains in bone density after treatment. The new study is currently in the design phase and funding phase and precise details are not yet available.

Statistical Analysis Plan

2.A. Statistical Analysis Plan Our aims in this protocol are as follows:

Aim 1: To establish the efficacy and safety of 6 months of TPTD versus placebo in premenopausal women with IOP

Aim 2: To determine the effect of 3 months of TPTD on bone remodeling at the tissue level and the extent to which baseline and 3 month bone remodeling predicts response to TPTD in premenopausal women with IOP.

Aim 3: To determine the extent to which 12 and 24 months of TPTD improves areal and volumetric BMD, bone microarchitecture and strength (stiffness) compared to baseline measures in premenopausal women with IOP

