Secondary safety outcome analyses: Fisher's Exact test will be used to assess treatment group differences in numbers of people endorsing each symptom reported on the symptom checklist administered at each study visit without adjustment for multiplicity. The GEE test approach proposed for the primary safety

outcome analysis of longitudinal events will be repeated for any symptom reported by >10% of either treatment group.

AIM 2:

Primary analysis: The between-group mean difference in the quad-labeled histomorphometric measured change in Mineralizing Surface (MdPm) and Bone Formation Rate (BFR/BS) at 3 months will be analyzed with ANCOVA with adjustment for the baseline continuous variables of age (years) and weight (kg.). Outcomes will be analyzed separately without adjustment for multiplicity. Secondary analyses: In the teriparatide-treated group the relationship between baseline MdPm and BFR/BS, and change in MdPm and BFR/BS in the first three months of treatment, and 12 and 24 month change in aBMD of the spine and hip by DXA and vBMD of the spine by cQCT will be assessed with multiple regression analysis. Per annum change in DXA and cQCT outcomes will be separately modeled as a function of baseline MdPm and BFR/BS, baseline level of the DXA or cQCT outcome, age, weight, bone microstructure by microCT of biopsy specimens, and change from baseline in MdPm and BFR/BS during the first three months. Other potential baseline predictors of DXA and cQCT response to teriparatide treatment will be explored with multiple regression to determine whether any clinical or constitutional measures supercede change in MdPm or BFR/BS in predicting bone change.

AIM 3:

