Primary efficacy outcome: For the primary endpoint of between-group difference in LS BMD at 6 months, power calculation assuming the proposed two-group ANCOVA and outcome correlation with baseline covariates of 0.3, we will have >90% power to detect a difference of $3.7 \pm 3.3\%$ in the TPTD-treated vs. $0.8 \pm 2.9\%$ in the placebo-treated group (placebo estimate based on interpolation from our preliminary data at 12 months). The estimated effect size is consistent with an annual TPTD-induced increases of 7.0-13.5% in studies by Arlot et al. in postmenopausal women, Langdahl et al. in premenopausal women with GIOP, and Kurland et al. in male IOP³⁶.

Primary safety outcome: For our primary safety outcome, the between-group difference in the number of people in each assigned group reporting at least one hypercalcemia or hypercalciuria event, we do not expect to have sufficient power to detect group differences in event rate because of the rarity of TPTD-related safety events observed in our pilot study and reported by others in the literature. Secondary efficacy outcome: For our secondary efficacy endpoints of between-group differences in TH, FN and 1/3R, our preliminary data suggest that we will not have sufficient power to detect between groups differences in these measures at 6 months, as the increases are less pronounced than at the LS. Secondary safety outcome: While we will closely examine the safety data, our small sample size provides minimal power to detect any but the most dramatic differences in safety profile between groups.

AIM 2:

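### Aim 2 asks whether turnover predicts response to teriparatide but tests this only in treated women, so a prognostic association cannot be told from a modified drug effect

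*Combined protocol and SAP*

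**What the plan says.** Section 1 names as a secondary aim "to determine whether baseline bone turnover, as assessed by quadruple tetracycline labeling predicts response to TPTD". Section 2.A repeats it under Aim 2 and widens it to 3-month remodeling: "the extent to which baseline and 3 month bone remodeling predicts response to TPTD in premenopausal women with IOP".

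The matching analysis is in section 2.A, Aim 2, Secondary analyses. Its population and predictors are "In the teriparatide-treated group the relationship between baseline MdPm and BFR/BS, and change in MdPm and BFR/BS in the first three months of treatment", and its outcomes are "12 and 24 month change in aBMD of the spine and hip by DXA and vBMD of the spine by cQCT". On the model: "Per annum change in DXA and cQCT outcomes will be separately modeled as a function of baseline MdPm and BFR/BS", together with the baseline value of the outcome, age, weight, biopsy microstructure and the 3-month change in turnover. Neither treatment arm nor an arm-by-turnover product is among the terms. The search for other predictors at the end of that paragraph, and the exploratory predictor analyses under Aim 3, plan no untreated comparison either.

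The placebo control is short: "At the 6 month timepoint, all subjects will receive TPTD" (section 2). Up to that point the data for a controlled comparison are collected in both arms. The first label set is completed before randomization (section 3.A, Visit 2), the quadruple-label biopsy is done at 3 months in Groups A and B, and DXA is repeated every 6 months (section 2).

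**The concern.** Response to a drug is the difference between what happens on it and what would have happened without it. A slope of BMD change on turnover among treated women is the sum of two parts: the slope that would exist without the drug (prognostic) and the extra slope due to the drug (effect modification). The planned regression estimates only the sum.

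If high-turnover women gain more or less bone whatever they receive, the regression will show a relation with turnover even when teriparatide works equally well at every level of it. Reported in the words of the aim, that would suggest that turnover can be used to choose whom to treat. The trial has a randomized arm that could separate the two parts at 6 months, and the plan does not use it for this question.

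**Working it through.** **Inputs from the documents.** Allocation 28 v 13 (section 2). Two-sided 5% alpha (section 2.A). Up to three covariates in the Aim 2 regression and 10% drop-out (section 2.B), which leaves 28 × 0.9 ≈ 25 and 13 × 0.9 ≈ 12. Six-month lumbar spine change of 3.7% (SD 3.3) on TPTD and 0.8% (SD 2.9) on placebo (section 2.B, Aim 1).

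**Assumed.** The correlation r between turnover and BMD change, which the documents do not give. It is varied from 0.3 to 0.74. The upper values match the plan's stated detectable variance of 40% to 55%: √0.40 = 0.63 and √0.55 = 0.74. Data are taken as normal and turnover is standardized.

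**The plan's own figure.** Section 2.B says that 40% to 55% of variance is detectable with 80% power. For one predictor after three covariates, the noncentral F test (λ = n·R²/(1 − R²), error df = n − 5) gives 23% at n = 28 and 26% at n = 25. Two predictors give 28–31% and four give 35–39%. The stated range is not reproduced. That is a separate matter, and nothing below depends on it.

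**Case 1: turnover purely prognostic.** Formula check at r = 0.5, n = 28: f² = 0.25/0.75 = 0.333, λ = 28 × 0.333 = 9.3 on 1 and 23 df, power 83%. The same formula gives 36% at r = 0.3 and 98% at r = 0.63. It treats predictor values as fixed. Simulation with random predictors gives somewhat lower figures, and those are used here (runs differ by a point or two):

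| r in both arms | Treated-only test, n = 28 | Treated-only test, n = 25 | Arm interaction |
|---|---|---|---|
| 0.3 | 32% | 29% | about 4–5% |
| 0.5 | 75% | 70% | about 4–5% |
| 0.63 | 94% | 91% | about 4–5% |

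If the slope rather than the correlation is held equal across arms, the interaction rejects in about 3–4%.

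**Case 2: turnover modifies the drug effect, with no slope on placebo.** At 28 v 13 the treated-only test is significant in about 75% of trials at r = 0.5 and 95% at r = 0.63. These are practically the Case 1 figures, so the planned test gives the same answer in both situations.

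**What the interaction could deliver under Case 2.** The value 0.48 is √0.234, the correlation at which the formula gives 80% power for the treated-only test at n = 28.

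| r on TPTD (0 on placebo) | Power, 28 v 13 | Power, 25 v 12 |
|---|---|---|
| 0.48 | 29% | 27% |
| 0.63 | 53% | 49% |
| 0.74 | 72% | 67% |

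The standard error at 28 v 13 is about 0.9 to 1.1 percentage points per SD of turnover. With 41 − 7 = 34 error df (t = 2.03), the 95% interval is about ±1.8 to ±2.2 points per SD, against a planned mean difference of 3.7 − 0.8 = 2.9 points.

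**The case against.** The strongest reply is that this is a secondary analysis in a study that calls itself exploratory, that no untreated comparison exists when the outcomes of interest are measured, and that a 6-month interaction with 13 placebo women may have under 30% power. A null result could be misread as proof that turnover does not matter. Parts of the text are also already worded suitably: the Aim 2 paragraph ends by speaking of predicting bone change, and section 2.B speaks of the predictability of DXA and cQCT changes. All of that stands. It limits the remedy to an exploratory estimate and a wording rule. It does not make a treated-only slope a measure of response, and the aims in sections 1 and 2.A still use that word. Reading the treated group to include Group B after the switch adds women but no untreated comparison.

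The rates are conditional. At r = 0.3 the treated-only test is significant in only about a third of trials. If the Bonferroni rule for secondary efficacy analyses covers these regressions, two tests at n = 25 bring the formula's figure at r = 0.5 down to 68%, from 83% unadjusted at n = 28.

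A reader might go further and infer from the planning SDs that 2.9²/3.3² = 77% of the variance on TPTD is unrelated to the drug, leaving at most 23% for differences in response. The documents do not support that split:
- Section 2.B describes the placebo figure as interpolated from 12-month data, while section 11 gives the same 0.8 ± 2.9% for women followed for an average of 4 years.
- The SDs include measurement error, which turnover cannot predict.
- The split assumes that drug response varies independently of untreated change.
- It sets 6-month SDs against a target for 12- and 24-month change.

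Nor do the documents show that turnover is in fact prognostic. The point is that the plan could not tell.

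**Conclusion.** The point holds as a mismatch between aim and analysis. The planned regression can show that turnover is associated with BMD change during treatment; it cannot show that turnover predicts response to teriparatide. The structural claim needs no numerical assumption. The size does: if turnover is purely prognostic, a significant treated-only result would arise in roughly a third of trials at r = 0.3 and in more than nine in ten at r = 0.63, at n = 28 with three covariates and no multiplicity adjustment.

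The 3-month change in turnover is a further limit. It is measured after randomization and may itself be an effect of the drug, so a baseline-by-arm term does not rescue it, and those results can only be described as associations. The change is worth making because it is cheap and alters what may be concluded. It does not touch the primary efficacy or safety result.

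**What to change.** In section 2.A, Aim 2, Secondary analyses:

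1. Add one exploratory model of 6-month LS aBMD change in all randomized women, with terms for arm, baseline turnover, arm × baseline turnover, baseline LS aBMD, age and weight. Fit it separately for BFR/BS and MdPm. Report the interaction with its 95% confidence interval.
2. State in advance that a non-significant interaction is not evidence that turnover leaves the drug effect unchanged.
3. Reserve the language of predicting response for the interaction. Describe the 12- and 24-month treated-only slopes, and every result for 3-month change in turnover, as *associated with BMD change on TPTD*. Align the aim wording in sections 1 and 2.A.
4. Carry over whatever adjustment is adopted for the altered randomization. Section 1 reports 12 of the first 18 women on placebo and plans 1 of the remaining 23, so arm is tied to enrolment period in this model too.

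The cost is SAP text and one model form on data already planned, with no new visit, sample or procedure. The downside is a wide interval, available at 6 months only, that may settle nothing on its own.

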Prior to statistical analysis, all outcome and covariate data will be summarized with descriptive statistics, outliers examined, distributions identified and normalizing transformations applied where indicated. All of the above analyses will be based upon the intention-to-treat principle. The missing data mechanism (MCAR, MAR) for all outcomes and covariates will be assessed and, in the event of a non-ignorable mechanism, analyses will subjected to the methods of Diggle and Kenward³⁹ for continuous measures or Ibrahim and Lipsitz⁴⁰ for safety outcomes. Bone turnover markers will be log-transformed prior to analysis. Inferential testing will use a 5% two-tailed type I error rate with no adjustment for multiplicity taken for primary outcome analyses. Secondary efficacy analyses type I error rates will be adjusted by Bonferroni method whereas secondary safety analyses will not. In keeping with the objective of proposed exploratory analyses to generate data patterns consistent or inconsistent with improved bone quality, no adjustment for multiplicity will be taken. No interim efficacy analyses are planned. The statistical analysis plan will be modified to account for the adaptive randomization procedure, which is relevant to Aim 1 only.

AIM 1:

Primary efficacy outcome analysis: Analysis of covariance (ANCOVA) comparison of between-group (treated vs placebo) differences in mean change in LS aBMD (g/cm^2) by DXA from pre-treated baseline to 6 months of assigned treatment with adjustment for the following continuous baseline variables LS aBMD (g/cm^2), age (years) and weight (kg).

Primary safety outcome analysis: Fisher's Exact test of between-group difference in the number of people in each assigned group reporting at least one hypercalcemia or hypercalciuria event in the first 6 months of assigned treatment; followed by Cox proportional hazards model analysis of the between-group difference in the time-to-first hypercalcemia or hypercalciuria event; followed by GEE testing of the between-group difference in the temporal pattern of the repeatedly sampled hypercalcemia or hypercalciuria events in the first 6 months of assigned treatment.

Secondary efficacy outcome analyses: TH, FN and 1/3 Radius aBMD by DXA will analyzed by ANCOVA as described for the primary outcome, above.

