Primary efficacy outcome analysis: Analysis by linear mixed models for repeated measures (LMM_R) of the within-group (TPTD) change in LS aBMD (g/cm²) by DXA from pre-treatment baseline with repeated measures at 12- and 24-months. (This is a growth curve model testing the hypothesis that the temporal trajectory of within-subject change in outcome differs from a random process.) The model estimates the fixed effect of time, random effects for subject, error and the quadratic and cubic values of time entered as random effects, continuous covariates for age and weight at baseline and with an AR(1) covariance structure. The random effects for higher-order factors for time model monotonic and U-shaped components of the growth curve. Model estimated within-subject differences between specific timepoints will be assessed when the fixed effect of time is statistically significant. The LMM_R model will be repeated for LS trabecular vBMD by cQCT after 24 months of teriparatide. Secondary efficacy outcome analysis: The same LMM_R analysis proposed for Aim 2 primary outcomes

will be used for secondary efficacy outcomes of TH, FN and $1/3^{rd}$ RD aBMD by DXA and HRpQCT after 12 and 24 months, and cQCT after 24 months of TPTD. These analyses will also be used to explore the pattern of change in serum BTMs (P1NP and CTx), between baseline and 24 months. Exploratory analyses will also be conducted to determine whether clinical factors such as age, BMI, body composition, and aspects of the growth hormone axis may predict BMD response to TPTD.

2.B. Power and Sample Size

We have based our power calculations upon the preliminary data generated from our recent pilot study of 22 women with IOP who were treated with teriparatide for 24 months. Our power estimates are based upon 40 women randomized to TPTD or placebo (28:12) with data for analysis, assuming a 10% drop-out and an alpha level of 5%.

AIM 1:

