Primary efficacy outcomes: For MdPm and BFR/BS after 3 months of TPTD, we base our effect size assumptions on the Lindsay et al²⁸ estimates of changes from baseline to 1-month of cyclic TPTD treatment (assuming these measures are virtually unchanged over 3 months in the placebo treated group). Lindsay reports cancellous BFR/BS increased from 0.008 ± 0.006 to 0.027 ± 0.018 (a standardized effect size of 1.42) and cancellous MdPm from 1.33 ± 0.95 to 3.78 ± 2.53 after 1 month (a standardized effect size of 1.28). With the proposed sample size, we will have over 90% power to detect difference comparable or larger than the increase in bone formation detected by Lindsay after 1-month of treatment. Secondary analyses to assess the predictability of DXA and cQCT changes from baseline and 3-month changes in BFR/BS and MdPm: The proposed sample size enables us to detect between 40% to 55% of the variance accounted for in the 12- or 24-month DXA or cQCT change and the baseline to 3-month change in BFR/BS or MdPm (assuming 80% power, 5% alpha and a multiple regression model with up to 3 covariates partialled from both the bone density outcome and the histomorphometric predictor).

AIM 3:

Primary efficacy outcomes: For LS aBMD by DXA after 12 and 24 months of TPTD, we will have >86% power to detect changes from baseline. We based our estimate of LS aBMD at 12 months on our preliminary data, and at 24 months on the data of Graeff et al.⁴¹ who detected a 10.2% increase in aBMD over 24 months. We anticipate that the increase between baseline and 12 months will far exceed the increase from 12 to 24 months, which may not be statistically significant. For trabecular vBMD at the spine by cQCT after 24 months of TPTD, the work of Rehman et al.³², who detected an increase of 35% in vBMD, suggests that we will have power of >99% to detect within-group changes.

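### The Aim 3 spine BMD model lists only the baseline, 12- and 24-month scans: too few for its cubic time term, and it omits the 6- and 18-month on-drug scans that could explain drop-out

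*Combined protocol and SAP*

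**What the plan says.** Section 2.A, Aim 3, specifies a linear mixed model for the within-group change in lumbar spine (LS) aBMD since the pre-treatment scan, "with repeated measures at 12- and 24-months". It describes this as a growth curve: a fixed effect of time, random effects for subject and for quadratic and cubic time, and AR(1) covariance. The secondary DXA outcomes (TH, FN, 1/3 radius) are likewise to be analysed after 12 and 24 months.

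Section 2 sets the scan schedule: "aBMD by DXA and HRpQCT will be measured at baseline and at 6 month intervals". Group B starts TPTD at study month 6, and after the 12-month visit "those initially randomized to placebo (Group B) will continue for an additional 18 months", that is, to month 30. Table 1 has DXA at month 6, and Table 3 has it for Group B at study months 12, 18, 24 and 30. On a clock that starts at the first TPTD dose, scans at 0, 6, 12, 18 and 24 months are therefore scheduled in both groups.

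The opening of section 2.A promises intention-to-treat analysis, an assessment of the missing-data mechanism for every outcome, and a selection-model method if missingness is non-ignorable. Section 2.B assumes 10% drop-out and says of LS aBMD at 12 and 24 months: "we will have >86% power to detect changes from baseline".

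**The concern.** There are two difficulties. First, the listed occasions and the model do not fit together: a cubic growth curve needs at least four time points, and three are named.

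Second, a likelihood-based mixed model handles drop-out validly when the observed values that predict it are in the model. A woman who leaves between on-drug months 6 and 12 would contribute only her baseline, although she has an on-drug scan. If a disappointing scan made leaving more likely, the data would be missing at random with that scan in the model and missing not at random without it.

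The documents leave this route open. The blind is broken at month 12, withdrawing women are counselled on other treatments (section 14), and imaging results can go to the primary care provider (section 11). Aim 3 has no control arm, so any such bias passes straight into the reported gain.

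**Working it through.** **1. The plan's own figure.** The stated power of more than 86% cannot be reproduced, because section 2.B gives neither the 12-month effect nor an SD for the 12- or 24-month change. As a check on whether the test is fragile, take a one-sample t test, two-sided 5%, with non-centrality δ√n/σ. Use δ = 10.2% at 24 months (section 2.B) and δ = 7.0% at 12 months (assumed: the low end of the annual range cited there). The only on-drug SD given is 3.3%, at 6 months; 5% and 7% are also tried. The least favourable case (δ = 7.0, σ = 7, n = 25) gives 7.0 × 5 / 7 = 5.0 and power above 99%. At n = 36, power of exactly 86% would need σ of about 13.4% (12 months) or 19.6% (24 months). The tests are not at risk.

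**2. The cubic term.** At t = 0, 12 and 24, t(t − 12)(t − 24) = 0, so t³ = 36t² − 288t.
- At t = 12: 36 × 144 − 288 × 12 = 5184 − 3456 = 1728 = 12³.
- At t = 24: 36 × 576 − 288 × 24 = 20736 − 6912 = 13824 = 24³.

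The columns 1, t, t², t³ have rank 3 of 4 on three occasions and 4 of 4 on five. On the covariance side, three occasions supply 3 × 4 / 2 = 6 variances and covariances. An unrestricted matrix for random intercept, quadratic and cubic terms needs 6 parameters, and AR(1) with its variance needs 2 more: 8 against 6. Even with independent random effects it is 3 + 2 = 5 against 6. Five occasions supply 5 × 6 / 2 = 15.

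**3. Bias, by hand.** Suppose a fraction p leaves after the 6-month scan because of its value. The 12-month mean of those who stay is then too high by ρσ · p/(1 − p) · m, where ρ is the correlation of the 6- and 12-month changes, σ the SD of the 12-month change, and m how many SDs below the mean the leavers' 6-month changes lie on average. Take p = 5% (half of the planned 10%), ρ = 0.7 and σ = 3.3. If the lowest 5% leave, m = 2.06, and the bias is 0.7 × 3.3 × (0.05/0.95) × 2.06 = 0.25 points. Simulation of that case gave 0.22.

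**4. Bias, by simulation.** Assumed mean changes at 6/12/18/24 months are 3.7/7.0/8.6/10.2%, with 41 women and about 10% drop-out, half after the 6-month and half after the 18-month scan; 1,500 runs per setting. The bias of the 24-month gain, in percentage points, is:

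| 24-month SD, adjacent-scan correlation | Drop-out | 12/24 scans only | All scans |
|---|---|---|---|
| 3.3%, 0.7 | random | 0.00 | 0.00 |
| 3.3%, 0.7 | logistic in scan value | 0.19 | 0.02 |
| 3.3%, 0.7 | lowest values leave | 0.25 | 0.00 |
| 5%, 0.5 | logistic | 0.17 | −0.01 |
| 5%, 0.5 | lowest values leave | 0.22 | −0.04 |
| 5%, 0.8 | logistic | 0.30 | 0.01 |
| 5%, 0.8 | lowest values leave | 0.46 | 0.02 |

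Here all scan-dependent drop-out is driven by the scan. If only half of it is, with logistic slopes of 0.5 to 1.0 per SD, the bias is about 0.07 to 0.09; a further check over milder and stronger settings gave 0.04 to 0.24. Against the three-scan standard errors in the table's settings (0.53 to 0.83), the tabulated biases are about 0.2 to 0.55 of one standard error. With about 20% drop-out the bias is 0.3 to 0.9 points, but that is double what the plan assumes.

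**5. Precision.** With complete data and categorical time, the standard error of the 24-month change is the same with three or five scans. With 10% random drop-out, a generalised-least-squares calculation gives 0.682 against 0.675, about 1% smaller; the simulated ratios for 41 women are 0.985 to 0.999.

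**The case against.** Nothing in the plan says that the 6- and 18-month scans are excluded. A reader might infer a decision to discard two of every five scans, but the documents do not support that. The cubic term suggests that more occasions may have been intended, with 12 and 24 months named only as the reporting times. This stands, and it is why the point is about what the model lists. The text still names two follow-up occasions and needs correcting on either reading. The scans are also scheduled rather than held for every woman, since those who leave will lack the later ones.

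A reader might also infer that any drop-out after an interim scan biases the result. It does not: drop-out must depend on the value of that scan, and with random drop-out both versions are unbiased. No section gives a drop-out pattern or a scan-based withdrawal rule, so the scenarios above are assumptions.

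The near-zero bias with all scans holds because the simulated drop-out depends only on observed values. Drop-out driven by something unmeasured would bias both versions.

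Finally, section 2.A already provides a selection model for non-ignorable missingness, and section 1 calls the study exploratory. The fallback covers part of the problem, but it rests on assumptions that the data cannot test. It is weaker than using scans already held, and here the non-ignorability would come from the model's own list of occasions. The exploratory status keeps the point minor.

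**Conclusion.** The point holds as a minor, no-cost improvement. The mismatch between three listed occasions and a cubic time term is a matter of algebra and needs no assumption. The bias is conditional: about 0.05 to 0.3 points, and up to 0.5 in the most extreme setting, on a gain of about 10 at the planned 10% drop-out. It rests on assumed means, SDs and correlations and on drop-out that depends on the interim scan value.

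Two stronger readings should be set aside. The omission costs almost no precision, about 1% or less in most settings at 10% drop-out and nothing with complete data and categorical time. It also does not endanger the baseline-to-12-month or baseline-to-24-month test, where power stays above 99% for every SD tried from 3.3% to 7%.

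**What to change.** In section 2.A, Aim 3, state that the DXA models (LS primary; TH, FN and 1/3 radius secondary) use all scheduled scans at 0, 6, 12, 18 and 24 months since the first TPTD dose. For Group B these are study months 6, 12, 18, 24 and 30. Keep the 12- and 24-month contrasts as the reported estimates, and preferably treat time as categorical, which removes the need for the polynomial terms. In the same sentence, say whether the within-group analysis covers Group A alone (28) or all 41 women, since the text leaves this open. Keep the selection model as a sensitivity analysis. The cost is SAP wording only: no new scan, visit or patient.
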